** End of Treatment, End of Residual Period & End of Study: This combined visit should be scheduled 7-14 days after all trial medications are permanently stopped, to account for the residual periods for everolimus (7 days) and exemestane (5 days).

a x is the number of the treatment cycle

1. Tumour assessments will be performed according to institutional practices. Based on DBL primary analysis, images no longer need to be sent to central CRO and reviewed independently. The overall response only will be collected in the electronic CRF.
2. A patient diary will be given to the patient for continuous use through the trial. It should be given to the patient at the start of each cycle. The diary collects information about medication taken at home and provides reminders about fasting bloods and urine samples. At Visit 1 of each cycle and at EOT treatment compliance needs to be checked including compliance calculation
3. All serious adverse events, AESI and study drug related adverse events still ongoing at the end of treatment will be followed until resolution/stabilization
4. Everolimus and exemestane should be taken once a day at approximately the same time of day, following a meal. The tablets may be taken at home or in the clinic.
5. Pre-menopausal women:
 Serum and/or urine pregnancy testing to be performed on Day 1 of each cycle until the end of treatment and after EOT per institutional practice Hormone testing to include estradiol only on Day 1 of every odd number cycle starting at Cycle 3 and end of treatment. See [Section 5.2.3](#).

TABLE OF CONTENTS

TITLE PAGE	1
CLINICAL TRIAL PROTOCOL SYNOPSIS	2
FLOW CHART -No longer applicable per CTPv6.0	7
FLOW CHART- Reduced schedule per CTP v6.0 – Ongoing patients	12
TABLE OF CONTENTS	13
ABBREVIATIONS	17
1. INTRODUCTION	21
1.1 MEDICAL BACKGROUND	21
1.2 DRUG PROFILE	24
1.2.1 Xentuzumab	24
1.2.2 Everolimus	25
1.2.3 Exemestane	26
1.3 RATIONALE FOR PERFORMING THE TRIAL	26
1.4 BENEFIT - RISK ASSESSMENT	27
2. TRIAL OBJECTIVES AND ENDPOINTS	28
2.1 MAIN OBJECTIVES, PRIMARY AND SECONDARY ENDPOINTS	28
2.1.1 Main objectives	28
2.1.2 Primary endpoint	28
2.1.3 Secondary endpoints	28
[REDACTED SECTION]	
3. DESCRIPTION OF DESIGN AND TRIAL POPULATION	31
3.1 OVERALL TRIAL DESIGN AND PLAN	31
3.2 DISCUSSION OF TRIAL DESIGN, INCLUDING THE CHOICE OF CONTROL GROUP(S)	32
3.3 SELECTION OF TRIAL POPULATION	33
3.3.1 Main diagnosis for trial entry	33
3.3.2 Inclusion criteria	34
3.3.3 Exclusion criteria	35

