The 1280-0022 phase II trial recently completed primary endpoint analysis and showed no added benefit of xentuzumab compared to placebo, in patients with everolimus and exemestane backbone therapy, when treating trial participants with metastatic breast cancer, HR+, HER2- and non-visceral disease. No new safety signals were observed with the addition of xentuzumab to the everolimus and exemestane combination.

In consideration of these top line results and in accordance with clinical trial protocol, as of 29 September 2021, Boehringer Ingelheim recommended to immediately discontinue xentuzumab and placebo administrations. Sites were also recommended to discontinue associated assessments related to primary endpoint assessments, including central imaging, central laboratory sampling and shipments and PRO questionnaires. Lastly, sites were advised that patients no longer needed to be followed for overall survival after they had completed the required safety follow up visits.

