The end of treatment (EOT) information has to be obtained when the trial treatment is permanently discontinued. EOT is defined as permanent discontinuation of all trial drugs. All patients who end the trial treatment for any reason other than progression of disease or start of further anti-cancer therapy will be followed for tumour assessment. All patients will be followed for drug-related serious adverse events/adverse events of special interest as described in the [Flow Chart](#) and [Section 6.2.3](#).

[figure not shown]

Figure 3.1: 1 Trial design

The primary PFS analysis for this Phase II trial will take place after approximately 40 patients have had an event of disease progression (independent assessment) or death; this is defined as the “Last Subject Last Visit Primary Endpoint” (LSLVPE). Patients will be followed up for OS (FU-OS) until all patients have completed treatment and attended the first follow-up visit (FU1). This time point is defined as the “Last Subject Last Visit Secondary Endpoint” (LSLVSE).

Note if at the time of LSLVPE the trial meets a pre-defined criterion (to be defined in the DMC charter) the trial will be expanded seamlessly into a confirmatory Phase III trial, changes to the LSLVPE and LSLVSE will be provided in a protocol amendment.

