5.2.7 Safety assessment as of 29 Sept 2021

As of 29 September 2021, all the safety assessments will be done according to local practice.

No follow-up information will be collected after patients discontinue study treatment except all AESIs, SAEs, related AEs still ongoing at the end of treatment, which will be followed until resolution/stabilization.

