6.2.3 Follow up period and trial completion

Not applicable as per CTP version 6. The end of study is defined as EOR/FUP1

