6.2.3.2 Follow-up for Overall Survival

All patients will be followed up for overall survival at 84 day (12 weeks) intervals until

- Death
- Lost to follow-up or
- Completion of the whole trial (as specified in [Section 8.6](#))

These visits may also be performed by e.g. telephone interview or via written correspondence in case the patient is unable to visit the investigator. The following information will be collected during the follow-up for survival period:

- Date and type of contact
- Post progression information including further anti-cancer treatment: regimen and drug name, start and stop dates, response to further anti-cancer treatment if available
- For each drug-related SAE/AESI, the investigator should provide the information with regard to concomitant medication and the medication administered to treat the

AEs on the appropriate CRF pages and the SAE form including trade name, indication and dates of administration

- Outcome event (record date of and reason for death, if applicable)
- Results from pregnancy testing (if applicable) see [Flowchart](#)

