8.6 TRIAL MILESTONES

The **start of the trial** is defined as the date when the first patient in the whole trial signs informed consent.

The **end of the trial** is defined as when the analysis of the LSLVSE (see below) is completed and patients have completed FU1 visit see [Section 3.3.4.1](#).

The **“Last Subject Last Visit Primary Endpoint”** (LSLVPE) is defined as the date when the required number of PFS events has occurred for primary endpoint analysis, see [Section 7.3](#).

The **“Last Subject Last Visit Secondary Endpoint”** (LSLVSE) is defined as the date when patients have completed FU1.

The **“Last Subject Last Treatment”** (LSLT) date is defined as the date on which the last patient at an individual trial site ends trial medication (as scheduled per protocol or prematurely). Individual investigators will be notified of SUSARs occurring with the trial medication until 30 days after LSLT at their site. **Early termination of the trial** is defined as the premature termination of the trial due to any reason before the end of the trial as

specified in this protocol.

Temporary halt of the trial is defined as any unplanned interruption of the trial by the Sponsor with the intention to resume it.

Suspension of the trial is defined as an interruption of the trial based on a Health Authority request.

The IEC / competent authority in each participating EU member state will be notified about the trial milestones according to the respective laws.

A final report of the clinical trial data will be written after the LSLVSE, see also [Section 7.3](#). Any data collected in this trial after this will be covered by a revision to the CTR.

The sponsor will submit to the EU database a summary of the final trial results within one year from the end of a clinical trial as a whole, regardless of the country of the last patient (EU or non-EU).

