5.2.2 Secondary endpoints

Overall survival

Overall survival (OS) will be calculated as the time from randomisation to death from any cause. Patients without evidence of death will be censored at the date of last contact when known to be alive.

Disease control

Disease control (DC), defined as a best overall response (BOR) of complete response (CR), partial response (PR), stable disease (SD) or Non-CR/Non-PD. SD and Non-CR/Non-PD must have been observed up until at least the Week 24 tumour assessment.

BOR is defined according to RECIST based on all evaluable tumour assessments from randomisation until the earliest of PD, start of subsequent anti-cancer therapy, loss to follow-up, withdrawal of consent or death. To be aligned with the primary endpoint derivation, tumour assessments after two or more consecutively missed assessments will not be considered.

Duration of disease control

Duration of DC will be calculated as the time from randomisation until the earliest of PD (according to RECIST) or death from any cause, among patients with DC.

The outcome rules defined in [Table 5.1: 1](#) will be used for the calculation.

Objective response

Objective response (OR), defined as a BOR (as detailed for DC) of CR or PR.

Time to pain progression or intensification of pain palliation

Time to pain progression or intensification of pain palliation, defined as the time from randomisation until the earliest of:

- ≥ 2 point increase from baseline in the Brief Pain Inventory – Short Form (BPI-SF), Item 3 (worst pain), without a decrease (of ≥ 1 point) from baseline analgesics use (via the 8-point Analgesic Quantification Algorithm [AQA]), or
- ≥ 2 point increase from baseline in the AQA, or
- Death

The rules to determine outcome (event or censored) along with the date of outcome are specified in [Table 5.2.2: 1](#). These rules will be applied to the independent assessment data prior to analysis.

[figure not shown]
In order to identify whether questionnaire assessments are missing, a nominal time-point based on the scheduling detailed in the CTP will be assigned to each assessment according to [Table 6.7: 2](#). If a patient does not have an assessment for both the BPI-SF, Item 3 and the AQA score at one of the scheduled time-points, it will count as a missed assessment;

[figure not shown]

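### Version 6 stops survival follow-up when treatment ends, yet the plan leaves room for a later OS analysis with no common data cut-off; such an update would be informatively censored

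*Protocol*

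**What the plan says.** **Text that ends survival follow-up.** Besides the Section 1.4 instruction ("patients no longer needed to be followed for overall survival after they had completed the required safety follow up visits"), three places in the current protocol do this:

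- Section 6.2.3, the parent of the OS follow-up section, reads: "Not applicable as per CTP version 6. The end of study is defined as EOR/FUP1".
- Section 5.2.7: "No follow-up information will be collected after patients discontinue study treatment except all AESIs, SAEs, related AEs still ongoing at the end of treatment".
- The reduced flow chart merges the last visits: "This combined visit should be scheduled 7-14 days after all trial medications are permanently stopped". It has no vital-status row; the superseded flow chart had one.

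**Text that keeps survival follow-up or a later analysis.**

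- Section 3.1: "Patients will be followed up for OS (FU-OS) until all patients have completed treatment and attended the first follow-up visit (FU1"), a time point it names LSLVSE.
- Section 6.2.3.2: "All patients will be followed up for overall survival at 84 day (12 weeks) intervals until" death, loss to follow-up or completion of the whole trial.
- Section 8.6 makes the end of the trial depend on completing the LSLVSE analysis, and adds: "A final report of the clinical trial data will be written after the LSLVSE".
- Section 7.3 foresees further data being collected and reported after unblinding.

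**The OS rules.** Section 7.3.2 lets OS run to the time point of a primary OS analysis and refers to Section 7.3, which names none. The tumour-based and pain endpoints in the same section stop at the primary PFS analysis. Protocol Table 7.5: 2 censors living patients at the last contact when known alive, and SAP 5.2.2 agrees: "Patients without evidence of death will be censored at the date of last contact when known to be alive". Neither document sets a calendar cut-off for OS.

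**The concern.** Two groups are treated differently after 29 September 2021. Patients already off treatment drop out of OS observation once their safety visits are done. Patients still taking everolimus and exemestane stay under observation until 7 to 14 days after they stop. Radiological progression is a listed reason for stopping (Section 3.3.4.1).

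From that date the OS risk set therefore consists of patients who are mostly progression-free, and each leaves around the time her prognosis is likely to worsen. Deaths after progression go largely unseen. Kaplan-Meier and Cox methods assume that censoring carries no information about the risk of death, and here it would.

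At stake is the tail of the survival curve, and any median read from it, if the report after LSLVSE re-estimates OS under the retained rules. OS is the first-listed secondary endpoint.

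**Working it through.** The plan states no figure on this point, so the check asks for the direction and size of the effect in an explicit model.

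**Inputs from the documents**

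- Median 9.9 months on control and 19.8 months on xentuzumab, 15 months of accrual, analysis at about month 30 (protocol 7.7).
- Last visit 7 to 14 days after the last dose, taken as 0.35 month (about 10.5 days).
- Median OS of 31.0 months on everolimus plus exemestane in the everolimus confirmatory trial, all patients (protocol 1.1).

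**Assumptions (not in the documents)**

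- Death hazard 0.003 per month before progression and m = 0.025 to 0.05 per month after it.
- Treatment stops at progression.
- 29 September 2021 falls at trial month 30 or 36. The documents do not give the interval from first randomisation to that date.

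**Model.** With progression hazard a = ln 2 / median, b = 0.003 and post-progression hazard m, true survival is

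S(t) = exp(-(a+b)t) + [a/(a+b-m)] × [exp(-mt) - exp(-(a+b)t)].

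For median 9.9 and m = 0.036: a = 0.0700 and a/(a+b-m) = 1.892. Then S(36) = 0.072 + 1.892 × (0.274 - 0.072), which is about 0.45. In the same way S(30) is about 0.54.

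**Version 6 follow-up.** Patients off treatment at the stop date are censored there. Patients on treatment are followed to progression plus 0.35 month. Kaplan-Meier estimates from a large simulation, minus the true value, in percentage points:

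| Median (months) | m | Stop month | 24 mo | 30 mo | 36 mo |
|---|---|---|---|---|---|
| 9.9 | 0.025 | 30 | +1.2 | +4.6 | +11.0 |
| 9.9 | 0.036 | 30 | +1.7 | +6.1 | +13.6 |
| 9.9 | 0.050 | 30 | +2.2 | +7.4 | +15.6 |
| 19.8 | 0.025 | 30 | +1.4 | +4.9 | +10.0 |
| 19.8 | 0.036 | 30 | +2.0 | +6.4 | +12.8 |
| 19.8 | 0.050 | 30 | +2.5 | +7.9 | +15.1 |
| 9.9 | 0.025 | 36 | +0.1 | +1.0 | +3.7 |
| 9.9 | 0.036 | 36 | +0.2 | +1.3 | +4.8 |
| 9.9 | 0.050 | 36 | +0.2 | +1.7 | +5.7 |
| 19.8 | 0.025 | 36 | +0.1 | +1.4 | +4.7 |
| 19.8 | 0.036 | 36 | +0.2 | +1.9 | +6.1 |
| 19.8 | 0.050 | 36 | +0.3 | +2.3 | +7.2 |

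**Check by hand (median 9.9, m = 0.036, stop at month 30).** Past 30 months from randomisation, everyone still at risk was on treatment at the stop date and dies at about 0.003 per month. The estimate therefore falls only from 0.60 to about 0.60 × exp(-0.018) = 0.59 by month 36. True survival falls from 0.54 to 0.45.

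**Comparator.** Censoring everyone at the stop date gives 0.54 at 30 months against a true 0.54, with the curve ending there.

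**Second calibration.** PFS median 9.9, OS median 31, stop at month 30. Results at 36 months, estimate against truth:

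- 5% of PFS events being deaths: 0.564 against 0.425. The estimated median is about 64 months instead of 31.
- 10% and 20% deaths: 0.54 against 0.43, and 0.50 against 0.44.
- 5% deaths, with 30% of patients treated four months past progression: 0.55 against 0.425.
- 5% deaths, with the stop date moved to month 24: 0.66 against 0.425. Here the 24-month value is also off, 0.696 against 0.620.

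**The case against.** The strongest reply is that no OS update is specified. Under protocol 7.3, if the expansion criterion is not met, the database is unblinded and the report covers primary, secondary and further endpoints. OS is therefore estimated at the primary PFS lock. The SAP is confined to that scenario (Section 3), and that analysis came before survival follow-up was dropped. Section 8.6 promises a final report, not a new OS curve, and defines LSLVSE only as completion of FU1, which fits version 6. On this view Sections 3.1 and 6.2.3.2 are leftover wording.

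Most of this stands. A reader might infer that the OS already reported is biased, or that the protocol schedules a biased re-estimate; the documents support neither. What survives is that OS alone has its own undefined analysis point, the LSLVSE analysis is retained, and no cut-off is set. Someone following the text could rerun OS at LSLVSE without breaking any written rule.

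A reader might also infer that patients are lost exactly at progression. They are lost 7 to 14 days after all trial medication stops. Treatment past progression is allowed (Section 6.2.2.2), and some stop for adverse events or by choice. This weakens the link but does not remove it.

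Finally, the arm with more patients on treatment might seem bound to get the more inflated curve. The table does not bear this out. At m = 0.036 and 36 months, the 19.8-month group has the smaller excess with a month-30 stop (12.8 against 13.6) and the larger with a month-36 stop (6.1 against 4.8).

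**Conclusion.** The point holds as a conflict in the current text and a conditional bias. OS at the primary PFS lock is sound on this count. An OS Kaplan-Meier estimate or hazard ratio that uses contacts after 29 September 2021 would be informatively censored.

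The upward direction rests on a higher death hazard after progression than before it, which is plausible but not quantified in the documents. Under the assumed hazards, the excess is about 1 to 8 points at 30 months and 4 to 16 points at 36 months for stop dates at month 36 to month 30. At 24 months it is at most about 2.5 points, provided the stop date is no earlier than month 30. The direction of bias in the hazard ratio cannot be determined.

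Sampling error is also large. With 40 patients in an arm, the standard deviation of the estimate at 30 months is about 10 points, more than the bias there. OS is unpowered, and without expansion no formal testing is done (protocol 7.2, 7.4, 7.7). Importance is minor to moderate.

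**What to change.** 1. Reconcile protocol 1.4, 5.2.7 and 6.2.3 with 3.1, 6.2.3.2 and 8.6, so that one statement says when OS follow-up ends and what the LSLVSE analysis contains.
2. In protocol 7.3 and 7.3.2 and SAP 5.2.2 and 7.5.2, state that the OS analysis is the one at the primary PFS database lock.
3. In the same places, state that any later OS estimate uses one administrative cut-off for all patients, no later than 29 September 2021. Patients known alive beyond it are censored at it, and later deaths are listed only.

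The cost is a few sentences and no new data collection. Some late follow-up time and a few deaths go unanalysed. In the second calibration with 80 patients and a month-30 stop, the average loss is about one death when 5% of PFS events are deaths (29.1 against 28.0) and about three when 20% are (33.1 against 29.7).

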2. TRIAL OBJECTIVES AND ENDPOINTS

2.1 MAIN OBJECTIVES, PRIMARY AND SECONDARY ENDPOINTS

2.1.1 Main objectives

This double-blind, placebo-controlled, randomised Phase II trial will be performed in female patients with HR+/HER2- advanced or metastatic breast cancer and non- visceral disease. The main objective of the trial is to assess the efficacy of xentuzumab in combination with everolimus and exemestane over everolimus and exemestane in this patient population. Efficacy will be assessed by determining whether or not the criterion for expanding the trial seamlessly into a Phase III trial is met. If the seamless option is met the trial will be expanded into a confirmatory Phase III trial with formal superiority hypothesis testing. If the seamless option is not met, the observed results will be evaluated in an explorative manner to see if they are sufficient for further development of this compound in this indication.

All imaging-related endpoints will be both independently assessed (in a blinded fashion) and investigator assessed according to RECIST 1.1 (see [Appendix 10.4](#)). The data from the independent assessments will be considered primary, with investigator assessment data as supportive.

2.1.2 Primary endpoint

The primary endpoint to determine efficacy of xentuzumab is progression-free survival (PFS) which is defined as time from randomisation until disease progression according to Response Evaluation Criteria In Solid Tumors (RECIST, version 1.1) or death from any cause, whichever occurs earlier.

[figure not shown]
2.1.3 Secondary endpoints

- Overall survival (OS) is defined as the time from randomisation until death from

any cause.

- Disease control (DC) is defined as a best overall response of complete response (CR), partial response (PR), stable disease (SD) or Non-CR/Non-Progressive Disease (Non-CR/Non-PD). SD and Non-CR/Non-PD must have a minimum duration of 24 weeks from randomisation. Best overall response is defined according to RECIST version 1.1 and will consider all tumour assessments from randomisation until the earliest of disease progression, death or last evaluable tumour assessment before start of subsequent anti- cancer therapy, loss to follow-up or withdrawal of consent.
- Duration of DC is defined as the time from randomisation until the earliest of disease progression or death, among patients with DC.
- Objective response (OR) is defined as a best overall response of CR or PR. Best overall response is defined according to RECIST version 1.1 and will consider all tumour assessments from randomisation until the earliest of disease progression, death or last evaluable tumour assessment before start of subsequent anti-cancer therapy, loss to follow-up or withdrawal of consent.
- Time to pain progression or intensification of pain palliation defined as the time from randomisation until the earliest of a clinically significant increase in pain (≥ 2 -point increase from baseline in the Brief Pain Inventory– Short Form [BPI-SF] Item 3) without a decrease in analgesics use, or intensification in pain palliation (≥ 2 -point increase in the 8-point Analgesic Quantification Algorithm [AQA]), or death.

** Note if the trial is expanded the secondary endpoint of OS is included in the statistical testing strategy in a hierarchical manner subsequent to significance being observed in the primary endpoint, for further details refer to [Section 7.2](#).*

3. DESCRIPTION OF DESIGN AND TRIAL POPULATION

3.1 OVERALL TRIAL DESIGN AND PLAN

This double-blind, placebo-controlled, randomised Phase II trial is designed to assess the efficacy of xentuzumab in combination with everolimus and exemestane compared to everolimus and exemestane alone in female patients with HR+/HER2- locally advanced or metastatic breast cancer and non-visceral disease.

If the criterion for the seamless option (to be defined in the DMC charter, prior to trial initiation) is met then the trial will be expanded into a confirmatory Phase III trial and remain double-blind. If the seamless option is not met, the observed results will be evaluated in an explorative manner to see if they are sufficient for further development of this compound in this indication (e.g. via a separate Phase III trial).

The trial will be performed by investigators specialised in the treatment of breast cancer. Patient inclusion will be based on locally confirmed HR+ and HER2-status. Archival tissue biopsies (most recent biopsy from initial diagnosis or metastatic setting) will be provided to retrospectively confirm HR+ and HER2-status by central assessment if possible. Provision of biopsy samples from the bone is not acceptable. Receptor status should be assessed by ASCO/CAP guidelines ([R15-6055](#), [R17-4255](#)). Patients must not have visceral metastases, i.e. metastases to lung, liver, pleura or peritoneum, malignant pleural or peritoneal effusions. Patients must not have evidence of brain metastases. Patients meeting all eligibility criteria will be randomised 1:1 to the experimental treatment arm containing xentuzumab or to the placebo control arm of the trial ([Figure 3.1: 1](#)). Patients will be treated in 28-day cycles until the end of cycle 20 (week 80) and in 56-day cycles from Cycle 21 (week 80) until they have PD, occurrence of intolerable AEs or withdraw consent. Patients will be randomised in blocks, treatment will be double blinded and randomisation will be stratified by the presence of bone-only metastases (Yes/No), and prior CDK4/6 inhibitor treatment (i.e. palbociclib, ribociclib, abemaciclib) (Yes/No). Use of xentuzumab or placebo beyond radiological progression will be allowed if deemed beneficial by the investigator and agreed with the patient. PFS as assessed by an independent blinded review according to RECIST 1.1 will be the primary endpoint. Safety and tolerability will be assessed by incidence and severity of adverse events according to CTCAE version 5.0 ([R18- 1357](#)). PK sampling and monitoring of anti-drug antibodies (ADAs) and neutralising antibodies (nAb) will be conducted throughout the trial in both treatment arms. Patients' safety, pattern of their disease progression and post progression information will be monitored throughout the trial by an independent DMC (see [Section 8.7](#)).

The end of treatment (EOT) information has to be obtained when the trial treatment is permanently discontinued. EOT is defined as permanent discontinuation of all trial drugs. All patients who end the trial treatment for any reason other than progression of disease or start of further anti-cancer therapy will be followed for tumour assessment. All patients will be followed for drug-related serious adverse events/adverse events of special interest as described in the [Flow Chart](#) and [Section 6.2.3](#).

[figure not shown]

Figure 3.1: 1 Trial design

The primary PFS analysis for this Phase II trial will take place after approximately 40 patients have had an event of disease progression (independent assessment) or death; this is defined as the “Last Subject Last Visit Primary Endpoint” (LSLVPE). Patients will be followed up for OS (FU-OS) until all patients have completed treatment and attended the first follow-up visit (FU1). This time point is defined as the “Last Subject Last Visit Secondary Endpoint” (LSLVSE).

Note if at the time of LSLVPE the trial meets a pre-defined criterion (to be defined in the DMC charter) the trial will be expanded seamlessly into a confirmatory Phase III trial, changes to the LSLVPE and LSLVSE will be provided in a protocol amendment.

